#### Study design

[figure not shown]
The study is an international multicenter prospective observational cohort study with a comparison cohort. Included are fetuses with a diagnosis of aortic stenosis who satisfy inclusion/exclusion criteria between 23+0 and 31+6 weeks of gestation. The decision whether a fetal balloon dilatation shall be attempted is not part of the study protocol. The number of examinations of mother/fetus/infant in this study is not different from the number of examinations that will be recommended for someone choosing not to be part of this study. The participation in the study is not affecting the treatment mothers and fetuses are receiving during pregnancy, nor how the infant is examined and treated after birth. The aim of the study

is to, in a prospective and organized way, collect and evaluate multi-center data in order to reduce the risk for selection bias, missing data and inter-variability between participating centers.

Cases will be recruited from centers offering fetal aortic valvuloplasty and and from centers not offering this treatment. Intervention cases will be recruited from high volume intervention centers. Fetal and postnatal echocardiographic examinations will be reviewed and remeasured by a core laboratory to confirm eligibility for inclusion, and identify potential measurement errors.

[figure not shown]
Data from two fetal echoes and one postnatal will be collected and each contains a comprehensive set of two-dimensional and Doppler measurements which will enable analysis of cardiac growth and development during pregnancy. Analysis of change of dimensions of the left heart structures and selected hemodynamic variables from the point of study inclusion until just before the first postnatal catheter or surgical procedure provides an opportunity to make a comparison between the groups that is unbiased with respect to centerspecific postnatal treatment policies.

Three echocardiographic examinations and a 2-year follow-up regarding patient outcome will be performed as per Figures 1-3 below.

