#### **Inclusion criteria**

The inclusion criteria will be identical in the intervention and the non-intervention cohorts. A modification of the inclusion criteria published by the group in Boston (2) and by the group in Linz (3) will be used. The modification is based on the retrospective study (9,10) and represent the currently used criteria for intervention.

- A. All of the following echocardiographic criteria need to be satisfied between 23+0 and 31+6 weeks (z-scores according to Schneider et al (13)):
- 1. Aortic valve stenosis with antegrade flow through the valve
- 2. Predominantly left-to-right shunt at the atrial level

- 3. Predominantly retrograde flow in the aortic arch between the first two brachiocephalic vessels
- 4. Qualitatively depressed left ventricular function
- 5. LV end-diastolic diameter Z-score  $> \pm 0$
- 6. Left ventricular inlet length in diastole :
  - a. Gest age  $\leq 24+6$ : Z-score  $> \pm 0$
  - b. Gest age 25+0 to 27+6: Z-score > -0.75
  - c. Gest age  $\geq 28+0$ : Z-score > -1.50
- 7. Mitral valve diameter in diastole Z-score > -2.0
- B. All of the following postnatal treatment options need to be available:
  - 1. Surgical or catheter based aortic valvotomy
  - 2. Ross-Konno surgery
  - 3. Norwood or hybrid stage-one surgery

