#### **Core laboratory**

Echocardiographic exams will be uploaded to a core laboratory FTP server managed by University of Gothenburg (IT Department, [contact]). A data transmission form (DTF) should be included with each submitted exam containing data on MediCasegenerated patient code, date of upload to server, make and model of the ultrasound machine and name of echocardiographer.

The core lab will have an audit function. Echocardiographic variables will be reported to MediCase by the submitting centre and measurements will be repeated on uploaded echoes by core lab without knowledge of submitted data. Submitted measurements differing by more than 20% from corresponding core lab measurements will be re-measured by a second reviewer, the core lab PI. If there is continued disagreement core lab will contact the submitting centre for a review of the original measurement and if this was in error the submitted value will be replaced by the core lab value provided that the image quality is acceptable. If that is not the case the value will be excluded from analysis. A similar approach will be used for variables based on qualitative or semiquantitative measurements such as magnitude of regurgitant jets on Color Doppler and ventricular function.

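### The centre's own echo reading is the default analysis value; the core-lab reading, taken blind to it, should be used instead, and should settle eligibility where the two disagree

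*Protocol*

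**What the plan says.** The Protocol, Core laboratory, states: "The core lab will have an audit function". Centres enter their own echo values, and "measurements will be repeated on uploaded echoes by core lab without knowledge of submitted data". Further action starts only above a tolerance: "Submitted measurements differing by more than 20% from corresponding core lab measurements will be re-measured by a second reviewer". If the second core-lab reading still disagrees, the centre is asked to look again, and "if this was in error the submitted value will be replaced by the core lab value provided that the image quality is acceptable". The next sentence adds: "If that is not the case the value will be excluded from analysis". Nothing is prescribed for differences of 20% or less. Qualitative variables are to be handled similarly, with no threshold given.

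On eligibility, the Protocol (Study design) says that examinations are "reviewed and remeasured by a core laboratory to confirm eligibility for inclusion", and SAP 1.2 repeats this. The entry limits are z-scores. For inlet length the limit falls with gestational age, for example "Gest age 25+0 to 27+6: Z-score > -0.75", with 0 for younger fetuses and -1.50 for older ones. SAP 2.1.1 keeps wrongly included cases out of FAS_ENR.

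SAP 3.1 lists baseline left ventricular diameter, inlet length, mitral and aortic diameters and LV:RV length ratio as potential confounders. SAP 4.1 and 4.6.1 carry these into the adjusted logistic model and the propensity score. SAP 3.5.1 and 4.1 use echo values for the growth analysis. None of these sections says whether the centre's or the core lab's value is analysed.

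**The concern.** The Protocol's Background names self-reported echo data as a limitation of the earlier comparative study, and Study design aims to reduce variation between centres. Yet the centre's value remains the default although a central reading will exist.

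This matters because centre and group go together. FAV cases come only from high-volume intervention centres. No-FAV 1 cases come only from centres that neither perform nor refer for the procedure, and the sample size section expects no-FAV 2 to be the smaller control group. If centres in one group tend to measure larger, adjusting for measured heart size compares fetuses whose true heart sizes differ. The primary odds ratio would then be biased even with every confounder in the model. Measuring hospital is recorded (SAP 3.1) but not marked as a potential confounder. The one centre variable so marked is the case volume of the intervening centre, which has no evident value for a fetus without an intervention.

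**Working it through.** **Plan's own figures.** The 20% tolerance is a rule, so there is nothing to reproduce. The planned 100 v 50 fetuses and the 30% control success rate are taken from the Protocol's sample size section. Its power of 91.8% (60% v 30%, two-sided Fisher's exact test) comes out at 92.7% by exact enumeration and is not in dispute.

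**Step 1: the tolerance in z units.** The tolerance is read as applying to the raw measurement, because a percentage of a z-score near zero has no meaning. For a fetus near the mean, z units = percentage difference / between-fetus coefficient of variation (CV). The CVs are assumptions.

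| Assumed CV | 20% difference | 10% difference |
|---|---|---|
| 8% | 20/8 = 2.5 z | 1.25 z |
| 10% | 20/10 = 2.0 z | 1.0 z |
| 15% | 20/15 = 1.3 z | 0.67 z |
| 20% | 20/20 = 1.0 z | 0.5 z |

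The step between successive inlet-length limits is 0.75 z (0, -0.75, -1.50). The tolerance exceeds it in every row. On a log scale the 20% figures run from 2.28 z (CV 8%) to 0.92 z (CV 20%), still above 0.75.

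**Step 2: how often the audit reacts.** Assume a centre reads 10% large on average and the centre-minus-core difference is normal with SD s. The share flagged is 1 - [Φ((20 - 10)/s) - Φ((-20 - 10)/s)]:
- s = 5%: 1 - Φ(2) = 2.3%
- s = 8%: 1 - Φ(1.25) = 10.6%
- s = 10%: 1 - Φ(1) + Φ(-3) = 16.0%

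Between 84% and 98% of that centre's values would stand unexamined.

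**Step 3: effect on the adjusted odds ratio.** Let logit(success) = a + b × (true z), with no treatment effect. Suppose FAV centres read d larger, so measured z = true z + d × FAV. Substituting gives logit(success) = a + b × (measured z) - b × d × FAV. The spurious FAV odds ratio is exp(-bd), that is, (outcome OR per z) to the power -d.

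| Outcome OR per z (assumed) | d = 0.5 | d = 1.0 |
|---|---|---|
| 1.5 | 0.82 | 0.67 |
| 2.0 | 0.71 | 0.50 |
| 2.5 | 0.63 | 0.40 |

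An offset of 0.5 z is 4% to 10% of the measurement for CVs of 8% to 20% (0.5 × 8 to 0.5 × 20), well inside the tolerance. If FAV centres read small instead, the ratios invert: 1/0.82 = 1.22 and 1/0.71 = 1.41 at 0.5 z, favouring FAV.

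Simulation with 100 v 50 fetuses, no effect, 30% success at mean z and OR 2 per z gave false-positive rates of 4.6% with no offset, about 13% to 16% at 0.5 z (two runs) and 36% at 1.0 z. Adding reading error (SD 0.4 z) and selection at an entry limit gave, at 0.5 z, an OR of 0.81 to 0.82 (OR 1.5 per z) and 0.73 to 0.76 (OR 2 per z). With core-lab values for entry and adjustment, the OR was 0.98 to 1.02 and false positives 4% to 6%.

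**Step 4: overlap of centres.** All of Step 3 assumes that no control is measured at a FAV centre. If 40% of controls share the FAV centres' reading habit (assumption), the average offset between groups falls to 0.6 × d. At d = 0.5 the OR is then about 1.5^(-0.3) = 0.89 or 2^(-0.3) = 0.81. With reading error and entry selection it is 0.91 or 0.85, with false positives of 4% to 6%.

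**Step 5: eligibility.** Study design and SAP 1.2 give the core lab the task of confirming eligibility. The Core laboratory section gives the only rule for disagreement, and it is triggered by 20%, not by which side of a limit a reading falls on. SAP 2.1.1 depends on the answer but does not supply it.

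**The case against.** **Eligibility.** A reader might infer that centre values govern entry and that a fetus failing on the core-lab reading stays in. The documents do not say so: the core lab re-measures to confirm eligibility. What stands is that no rule names the deciding value.

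**Values above 20%.** A reader might infer that a disputed value is kept unless the centre admits error. The text does not make replacement depend on the centre's agreement, and the exclusion sentence may mean that unresolved values are dropped. What that sentence refers back to (error, image quality or both) is unclear. It does not touch differences within 20%.

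**Values from a biased centre.** It would also be wrong to say that such a centre is never corrected. Some of its single values are flagged, as Step 2 shows.

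**Size.** The larger biases need a full 1 z offset and complete separation of centres by group. No-FAV 2 can come from the same high-volume centres, and each group may pool centres with differing habits. SAP 4.1 also adjusts for a candidate confounder only if p<0.10 for both group and outcome, which lowers the bias slightly. These points stand, and they reduce the expected size without removing the mechanism.

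**Growth.** The outcome is change from baseline, so a constant offset partly cancels if one centre measures both echoes. The analysis is exploratory and outside the confirmatory sequence. This stands, though hospital is recorded for each echo separately, so a common measuring site is not assured.

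**Remedy.** Centre values would remain where images are too poor for the core lab, so two sources are mixed. If image quality differs by group, some bias returns. That is a reason to count such values by group.

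**Conclusion.** The concern holds as a risk that can be reduced cheaply, not as a demonstrated bias. The centre's value is the default for confounders, propensity score and growth, and the 20% tolerance is wide on the z scale for every CV assumed (2.5 to 1.0 z for CVs of 8% to 20%). The audit would miss most values from a centre that reads consistently 10% large.

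A 0.5 z offset gives an adjusted OR of about 0.8 to 0.7 for outcome ORs of 1.5 to 2 per z under no effect and full separation of centres, and about 0.9 to 0.8 if 40% of controls share the FAV centres' habit. The sign depends on which centres read larger. A reader might conclude that the primary result will be biased, or biased against FAV. The documents give no evidence on the size, sign or existence of an offset, so neither conclusion follows. The CVs, reading-error SDs, offsets, outcome ORs and overlap are all assumptions. That the plan names no analysis value and no deciding value for eligibility rests on the text alone.

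**What to change.** In the Protocol's Core laboratory section and in SAP 2.1.1, 3.1 and 3.5.1:

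- Make the core-lab value the analysis value for confounders, propensity score and growth wherever image quality allows.
- Make it the deciding value for FAS_ENR eligibility under the same condition, so that readings on opposite sides of a z-score limit have a stated resolution.
- Where the core lab cannot measure, flag any centre value used and report the number of such values by group.
- State what the exclusion sentence refers to.
- Keep the 20% comparison as a quality check, and report centre-versus-core agreement by group.
- Repeat the primary analysis with centre values as a sensitivity analysis.

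The cost is wording and some analysis work, since the core lab already plans these measurements. A few borderline fetuses may leave FAS_ENR, and values on poor images will come from a mixed source.

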### Data analysis and statistical support

The main analysis comparing intervention versus non-intervention will be on an intention-totreat, i.e. intention to perform fetal aortic valvuloplasty, basis. Intention to perform fetal valvuloplasty is defined as being present if the needle has been introduced through the maternal abdominal wall even if the fetal thorax has not been touched. Subjects will be identified as belonging to the fetal aortic valvuloplasty (FAV) or the no-FAV groups as listed below.

The following study groups will be identified:

- Subjects that undergo a technically successful fetal aortic valvuloplasty at a high volume intervention centre (FAV 1).
- Subjects with intention-to-treat (according to the above definition) at a high volume intervention centre but with no technical success (FAV 2).
- Subjects counselled at a center not performing or referring for fetal aortic valvuloplasty (no-FAV 1).
- Subjects counselled at a high- or low-volume intervention center, or at a center offering referrals to a center performing interventions, and the parental decision is to not perform fetal aortic valvuloplasty (no-FAV 2).

The main analyses will be to compare FAV 1+2 versus no-FAV 1+2. The expected proportion of enrolled fetuses/infants will be 2 [FAV] : 1 [no-FAV]. Complementary analyses will be comparing FAV 1 versus no-FAV 1, and FAV 1 versus no-FAV 1+2.

Statistical support will be provided by Statistiska Konsultgruppen, Gothenburg, Sweden ([name]). Sample size will be calculated based on our previous retrospective study in combination with results published by the Boston group and by IFCIR (International Fetal Cardiac Intervention Registry).

The main analysis will be on an intention-to-treat basis. In this analysis fetal intervention cases, regardless of whether the intervention was technically successful or not, will be compared with non-intervention cases with regard to the primary outcome measure. Cox proportional hazards regressions and Kaplan Meier curves will be constructed, comparing survival between cohorts. Fetal left heart growth will be analyzed using descriptive statistics and will be compared between intervention and non-intervention groups from baseline fetal echo to the follow-up fetal and neonatal echo respectively.

In additon the same comparisons will be made after excluding the technically unsuccessful cases.

Cases with termination of pregnancy after study inclusion will be excluded from analysis but numbers noted.

Subgroup analyses will be performed for:

- Subjects with diagnosis of fetal aortic stenosis that undergo technically successful fetal aortic valvuloplasty and additional fetal cardiac intervention(s) such as atrial septal balloon dilatation or stent placement.
- b. Subjects with diagnosis of fetal aortic stenosis and hydrops.
- c. Subjects with diagnosis of fetal aortic stenosis, severe mitral regurgitation and left atrial enlargement with or without restrictive or intact atrial communication and with or without hydrops.

#### Sample size

The duration of this observational study will depend on the rate of inclusion. Based on our previous experience from a European retrospective study, and on the increasing prenatal detection rate of cardiac defects, it is estimated that 10-20 intervention cases can be included each year. Inclusion rate of non-intervention cases will depend on how many non-intervention

centers decide to join the study and on the proportion of subjects offered intervention who choose to refrain. It is projected that at least half as many non-intervention cases can be included each year. The study plans to end when 100 FAV cases are enrolled and at least 50 no-FAV cases, or 5 years from the first included patient, whichever occurs first.

The power calculations below are performed applying two-sided Fisher's exact test. The main analyses, however, will require adjusted analyses due to the study design being observational and not randomized. The confounders and their relation to the outcome and the main exposure variable are not completely known at the time of the study planning. Therefore, simplified power calculations were performed in order to assure that the study has potential to answer the main posed questions.

#### Inclusion of 100 intervention cases and 50 controls

The aim is to include at least 100 fetuses in the FAV 1+2 groups and 50 in the comparison group no-FAV 1+2. The largest numbers will likely be in FAV 1 and no-FAV 1 while the numbers in groups FAV 2 and probably also in no-FAV 2 will be smaller.

Assuming number of fetuses included as per above, 150 in total, and 30% success rate for the primary endpoint (=transplantation-free survival from fetal diagnosis to 2 years postnatal age, having a biventricular circulation without pulmonary hypertension at that time) in the no-FAV 1+2 group (9) and 60% success rate in the FAV 1+2 group, using alpha 0.05 and two-sided Fisher's exact test, a power of 91.8% would be able to be achieved. For a power of at least 80%, and all other assumptions unchanged, a success rate of 56% vs 30% in the FAV and no-FAV group, respectively, would be needed to be observed.

#### Inclusion of 100 intervention cases and 100 controls

Assuming number of fetuses included as per above, 200 in total, and 30% success rate for the primary endpoint in the no-FAV 1+2 group (9) and 60% success rate in the FAV 1+2 group, using alpha 0.05 and two-sided Fisher's exact test, a power of 98.7% would be able to be achieved. For a power of at least 80%, and all other assumptions unchanged, a success rate of 51% vs 30% in the FAV and no-FAV group, respectively, would be needed to be observed.

#### Statistical Analysis Plan (SAP)

All details of the statistical analysis are described in the statistical analysis plan (SAP).

## Ethics

The study was approved by the Ethical Review Board in Gothenburg (Dnr 050-18, 2018-04-26). Each participating institution/country (as required) will submit an application for ethical approval.

The consent form used for the ethical application in Sweden is available in an English version.

## **Publication of results**

The results might be reported in two separate papers depending on journal preferences. If so, the first paper will evaluate the safety of the prenatal procedure and the growth of the left heart structures from the point of study inclusion until just before the first postnatal surgical or catheter procedure as well as survival to and circulatory outcome at neonatal discharge. The second paper will evaluate transplant-free survival from fetal diagnosis to 2 years postnatal age, having a biventricular circulation without pulmonary hypertension at that time (primary outcome). Co-authorship will be based on the criteria published by ICMJE (18).

#### Funding

Swedish Heart-Lung Foundation (Grant no 20160786)

Grant from the Swedish state under the agreement between the Swedish government and the county councils, the ALF-agreement (Grant no ALFGBG-818681)

#### Significance and clinical relevance

The worldwide experience of fetal cardiac interventions has recently been reviewed (19-31). Best evidence of treatment efficacy should if possible be based on results provided by prospective double-blind randomized controlled trials. No such study has yet been performed. After careful consideration we have come to the conclusion that a randomized trial is not practical because of the rarity of the condition and because many pregnant women with a fetus having a severe cardiac defect such as aortic stenosis would likely be unwilling to accept randomization to fetal valvuloplasty. Also because the largest centers for fetal cardiac interventions in Europe are unwilling to participate in a randomized trial since, based on their experience, they feel that such treatment is beneficial. A strictly controlled prospective cohort study is a good alternative to a randomized trial. Data generated from this study will increase the evidence base for or against fetal aortic valvuloplasty . If the results show a treatment benefit the study will support continued development of fetal valvuloplasty in aortic stenosis. If on the other hand no treatment benefit can be shown, present programs of fetal aortic valvuloplasty may have to be reconsidered.

STATISTISKA KONSULTGRUPPEN Statistical Analysis Plan Protocol: Protocol No: Effect of fetal aortic valvuloplasty on outcomes Version: Version: 1.0 Page 3 of 26

.6	Efficacy Analyses	23
4.6.1	Primary Efficacy Analysis	23
4.6.2	2 Secondary Efficacy Analyses	23
4.6.3	3 Subgroup Analyses	24
.7	Safety Analyses	24
4.7.1	Fetal Left Heart Growth	24
4.7.2	2 Intervention and Technical Details	24
4.7.3	Complications of fetal intervention and maternal complications	24
4.7.4	Events	25
Inter	im Analyses	25
Char	nges of Analysis from Protocol	25
Listir	ng of Tables and Figures	25
' .1	Listing of Tables	25
.2	Listing of Figures	26
	4.6.1 4.6.2 4.6.3 4.7 4.7.1 4.7.2 4.7.2 4.7.2 Inter Chai Listin 7.1	 4.6 Efficacy Analyses

Statistical Analysis Plan

Protocol: Effect of fetal aortic valvuloplasty on outcomes

Version: 1.0 Page 4 of 26

List of abbreviations

Abbreviation	Definition
ВМІ	Body mass index
BSA	Body surface area
BV	Biventricular circulation
CI	Confidence interval
EDD	Estimated date of delivery
EFE	Endocardial fibroelastosis
eCRF	Electronic case report form
FASBIRTH	Full analysis set at birth population
FAS _{ENR}	Full analysis set enrolled population
FAV	Fetal aortic valvuloplasty
GA	Gestational age
GW	Gestational weeks
IUD	Intrauterine death
LA	Left atrium
MR	Mitral regurgitation
OR	Odds ratio
PHT	Pulmonary hypertension
PP	Per protocol
PPBIRTH	Per protocol at birth population
PP _{ENR}	Per protocol enrolled population
SDS	Standard deviation score
ТоР	Termination of pregnancy
UV	Univentricular circulation

TATISTISKA KONSULTGRUPPEN	Statistical Analysis Plan	
otocol: Effect of fetal aortic valvuloplasty on outcomes	Protocol No	:
	Version: 1.0	Page 5 of 26

List of definitions

Term	Definition
Gestational age	Gestational Age = (280 - (Estimated Delivery Date - Reference Date)) / 7. Reported as weeks and days of gestational age.
Biventricular circulation	The systemic circulation supported only by the left ventricle and the pulmonary by the right ventricle (+/-PFO/ASD)
Univentricular circulation	The systemic circulation supported completely or partly by the right ventricle
Absence of pulmonary hypertension	A TR max velocity ≤ 2.8 m/s with no other echocardiographic signs of pulmonary hypertension and/or catheter data showing a mean pulmonary arterial pressure <25 mmHg

Statistical Analysis Plan

